18.6.2 Efficacy Analyses

The efficacy analyses will be conducted using the ITT (primary analysis population), mITT, and PP populations. The efficacy parameters will be evaluated comparing the ibrexafungerp treatment group versus the placebo group.

The primary endpoint, the percentage of subjects with documented Clinical Success up to TOC (Week 24), will be analyzed using a Cochran-Mantel-Haenszel (CMH) test adjusted for site; p-values and 95% confidence intervals will be presented. Subjects whose results are missing at TOC (Week 24) will be imputed as failures in the analysis. In the event that model convergence is an issue with a stratified analysis, alternative

methods for accounting for site, or an unstratified analysis will be considered. A sensitivity analysis will be performed on the ITT population where subjects with missing values will be removed from the analysis.

For other continuous efficacy endpoints, a two-way analysis of variance (ANOVA) model will be used including effects for treatment and site; p-values and 95% confidence intervals will be presented. For other categorical endpoints, the CMH test adjusted for site will be performed, and p-values and 95% confidence intervals will be presented.

For the ordered categorical endpoint, a proportional odds model will be fitted accounting for the effects of treatment and site. The proportional odds model will fit an ordered regression model for the ordinal dependent variable as described by McCullagh (1980). If the assumption of proportional odds is violated alternative analyses will be considered which require a weaker assumption.

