#### **4.4. Handing of missing data**

##### **4.4.1. Non-Responder Imputation (NRI) for Categorical Responses**

For clinical responses which described in section 8.1, and 8.2.1, a subject who has not previously experienced a failure response of the endpoint of interest and does not have the required assessment of potential recurrence data at Week 4 (or Week 8, Week 12, Week 24 (TOC) and Week 36 (EOFU)) for any reason will be considered as failure in the analysis of the specified time point. If one or more of the required assessments of potential recurrence are not completed within Week 4 (or Week 8, Week 12, Week 24 (TOC) and Week 36 (EOFU)), the subject will be considered as failure. Randomized and took at least 1 study treatment patients without at least 1 post-baseline observation will also be defined as failure for the NRI analysis.

For mycological outcome, subjects will be considered a non-responder for the NRI analysis if their mycological outcome cannot be determined due to early termination before the specified visit or missing mycological data at the specific visit. Randomized subjects without at least 1 post-baseline observation will also be defined as non-responder for the NRI analysis.

Randomized subjects without study treatment will be excluded from all analysis.

The NRI may be applied at any time point specified for analysis.

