### 8.1. Primary Endpoint

The primary efficacy endpoint is defined as the proportion of ITT subjects who have documented Clinical Success (defined as subjects having a TOC evaluation and no Mycologically Proven, Presumed or Suspected Recurrences of VVC) up to Week 24 (TOC).

Clinical success will be assessed according to the following definitions:

- Clinical success: Subjects having a TOC evaluation and no Mycologically Proven, Presumed or Suspected Recurrences of VVC prior to or at the TOC visit.
- Clinical failure: Mycologically Proven, Presumed or Suspected Recurrences of VVC prior to or at the TOC visit. For the subject who early terminated before TOC visit, the subject is considered a clinical failure.

Recurrence of VVC: In this study, Recurrence of VVC will be broken into three categories:

- Mycologically Proven Recurrence: An episode of VVC with a total composite score  $\geq 3$  on the VSS Scale and a culture positive for *Candida* spp. that required antifungal treatment.
- Presumed Recurrence: An episode of VVC with a total composite score  $\geq 3$  on the VSS Scale that required antifungal treatment and for which there is a positive KOH microscopy but no positive fungal culture.
- Suspected Recurrence: An episode of VVC that required treatment with an antifungal agent (including self-administration with over-the-counter antifungals) regardless of VSS composite score but for which there is no mycological evidence of disease, such as a positive KOH microscopy or fungal culture. It also includes an episode of VVC that requires antifungal treatment and have a total VSS composite score lower than 3 regardless of mycological results.

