#### 8.1.1. Primary Analysis

The primary efficacy analysis will be performed on the ITT set at the TOC visit and will compare the proportion of subjects, in the treatment and placebo groups, who have documented Clinical Success up to Week 24 (TOC).

The number and percentage of subjects with documented clinical success up to the TOC visit will be presented by treatment group. Meanwhile, the number and percentage of subjects with clinical

failure will be presented by the recurrence categories. A Cochran Mantel Haenszel (CMH) test adjusted for Country and uncontrolled diabetes mellitus (Yes or No) at baseline will be performed to assess the statistical significance of a difference between treatment groups in the primary efficacy analysis. Mathematically stated:

$H_0$ : Clinical Success Rate up to Week 24 (TOC) Oral ibrexafungerp 300-mg dose = Clinical Success Rate up to Week 24 (TOC) Placebo

$H_1$ : Clinical Success Rate up to Week 24 (TOC) Oral ibrexafungerp 300-mg dose  $\neq$  Clinical Success Rate up to Week 24 (TOC) Placebo

The p-value, relative risk and 95% confidence interval (CI) will be presented in the ibrexafungerp 300-mg treatment arm compared to the placebo arm. Subjects who have one or more of the required assessments of potential recurrence not completed prior to or at Week 24 (TOC) visit or subjects who withdraw from the study early will be imputed using the imputation rules described in [Section 4.4.1](#).

A sensitivity analysis using the ITT set will be performed where subjects with the imputed clinical outcome will be removed from the analysis.

Subgroup analyses will be performed in the ITT set depending on BMI category ( $\leq 35$  kg/m^2 or  $>35$  kg/m^2), geographic region (USA and EX-USA), Race (White, Black or African American, Asian, American Indian or Alaska Native, Native Hawaiian or Other Pacific Islander, and Other), Uncontrolled diabetes mellitus (Yes or No), Ethnicity (Hispanic or Latino, Not Hispanic or Latino), Number of recurrent VVC episodes in the prior year ( $<4$  times,  $\geq 4$  times) and Candida species at screening (by Genus species), severity of VVC at screening (2 categorizations of the composite score of the vulvovaginal signs and symptoms at screening will be used to evaluate the severity of VVC at screening:  $<7$ ,  $\geq 7$  and '4 - 7', '8 - 12', and ' $\geq 13$ ').

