## 8.2. Secondary Efficacy Endpoints

### 8.2.1. Clinical Response

The same inferential analysis employing the same methods as for the primary analysis will be performed for ITT, mITT, and PP sets to assess below endpoints.

- The percentage of subjects with no Mycologically Proven Recurrence (defined as an episode of VVC with a total composite score  $\geq 3$  on the Vulvovaginal Signs and Symptoms [VSS] Scale and a culture positive for Candida spp. that required antifungal treatment) up to Week 4, Week 8, Week 12, Week 24 (TOC), and Week 36 (end of follow-up [EOFU]);

- The percentage of subjects with no Mycologically Proven, Presumed or Suspected Recurrences up to Week 4, Week 8, Week 12 and Week 36 (EOFU);
- The percentage of subjects with no Mycologically Proven or Presumed Recurrences up to Week 4, Week 8, Week 12, Week 24 (TOC) and Week 36 (EOFU);

For each specified timepoint, any clinical assessment outcomes at or before the specified visit will be counted. The imputation rules described in [Section 4.4.1](#) will be used for the NRI analyses.

Analysis of time to first recurrence (Mycologically Proven, Presumed or Suspected) and time to first Mycologically proven recurrence of VVC through EOFU will use Kaplan-Meier method to estimate the median recurrence time and its 2-sided 95% CIs based on the ITT, mITT, and PP sets. The time to first recurrence (Mycologically Proven, Presumed or Suspected) and time to first Mycologically proven recurrence of VVC is defined as time (days) from first dose of study drug to the first recurrence (Mycologically Proven, Presumed or Suspected) and first Mycologically proven recurrence of VVC, respectively. Subjects who completed the study will be censored at the last visit date if no previously recurrence of VVC experienced. Subjects who discontinued early will be censored at the last available assessment if no previously recurrence of VVC experienced. Subjects who missed any required assessment of potential recurrence will be censored at the last available assessment before the first missed assessment if no previously recurrence of VVC experienced. If there was no post-baseline assessment of potential recurrence, subjects will be censored at the first dose date of study treatment.

Kaplan-Meier curves for time to the first recurrence (Mycologically Proven, Presumed or Suspected) of VVC and time to first Mycologically proven recurrence will be provided by treatment group based on the ITT, mITT, and PP sets.

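### The primary endpoint's sensitivity analysis removes or keeps subjects with missing data according to whether they had already recurred, which inflates the relative risk under equal missingness and can mislead in either direction when dropout differs by arm

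*SAP*

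**What the plan says.** The primary endpoint is Clinical Success up to Week 24. SAP 8.1 defines success as having a TOC evaluation and no recurrence of any category by then. Its definition of failure begins "Clinical failure: Mycologically Proven, Presumed or Suspected Recurrences of VVC prior to or at the TOC visit".

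SAP 8.1.1 sends two groups to the imputation rule: early withdrawals, and "Subjects who have one or more of the required assessments of potential recurrence not completed prior to or at Week 24 (TOC) visit". The rule, in SAP 4.4.1, assigns failure to "a subject who has not previously experienced a failure response of the endpoint of interest and does not have the required assessment" of potential recurrence at the time point. It then adds a second trigger, which opens "If one or more of the required assessments of potential recurrence are not completed within Week 4" and continues to the later time points. One incomplete assessment is enough. SAP Appendix 1 schedules six such assessments through TOC (Weeks 4, 8, 12, 16, 20 and 24), of which Weeks 16 and 20 are phone contacts.

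The check on this rule is the SAP 8.1.1 sentence "A sensitivity analysis using the ITT set will be performed where subjects with the imputed clinical outcome will be removed from the analysis". Protocol 18.6.2 words it more broadly: "A sensitivity analysis will be performed on the ITT population where subjects with missing values will be removed from the analysis".

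**The concern.** A complete-case check is neutral under random missingness only if removal does not depend on the outcome. Here it does. Take two women who both withdraw at Week 14. One recurred at Week 9: she is an observed failure and stays in. The other had not recurred: her outcome is imputed and she is removed. The same split applies to two women who both miss the Week 16 call and both attend TOC. The recurrence-free one meets the SAP 8.1 definition of success, yet she counts as a failure in the primary analysis and is dropped from the check.

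This is the only sensitivity analysis specified for the primary imputation rule. If it carries a bias of its own, agreement or disagreement with the primary result cannot be read simply as showing how much the missing data matter.

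**Working it through.** **Inputs.** Success rates of 65% and 43% and about 240 subjects randomized 1:1 come from Protocol 18.1 and SAP 4.1. An exact two-sided Fisher calculation at 120 per arm gives power 0.909, so the plan's 90% is reproduced. The planning truth is a difference of 22.0 points and a relative risk of 0.65/0.43 = 1.51, the measure SAP 8.1.1 reports. Dropout and missed-contact rates are my assumptions.

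**Case 1: missed contacts, equal in both arms.** Each of six contacts is missed at random 5% of the time, and recurrences are still recorded. A recurrence-free subject is then removed with probability q = 1 - 0.95^6 = 0.265, and no recurred subject is removed. The analysed success rate is s' = s(1-q)/(1-sq).

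- Active: 0.65 × 0.735/(1 - 0.65 × 0.265) = 57.7%
- Placebo: 0.43 × 0.735/(1 - 0.43 × 0.265) = 35.7%
- Difference 22.0 points; relative risk 1.62

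The odds become s(1-q)/(1-s), so the odds ratio stays at 2.46. With 2% missed per contact the relative risk is 1.55. With 5% on the five pre-TOC contacts only, it is 1.60.

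**Case 2: dropout.** Assume a constant recurrence hazard and a fraction d dropping out at a uniform time, independently of recurrence. The probability of recurring before dropout is h = 1 - (1-s)/(-ln s).

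- Active: h = 1 - 0.35/0.4308 = 0.188
- Placebo: h = 1 - 0.57/0.8440 = 0.325
- Primary (missing as failure): (1-d)s
- Sensitivity: (1-d)s/[(1-d) + d·h]

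For example, at d = 10% the active arm gives 0.585/(0.9 + 0.0188) = 63.7%. At d = 30% the placebo arm gives 0.301/(0.7 + 0.0974) = 37.7%.

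| Dropout, active/placebo | Primary: difference, RR | Sensitivity: rates | Sensitivity: difference, RR |
|---|---|---|---|
| none | 22.0, 1.51 | 65.0 v 43.0 | 22.0, 1.51 |
| 10%/10% | 19.8, 1.51 | 63.7 v 41.5 | 22.2, 1.53 |
| 20%/20% | 17.6, 1.51 | 62.1 v 39.8 | 22.3, 1.56 |
| 30%/30% | 15.4, 1.51 | 60.2 v 37.7 | 22.4, 1.59 |
| 10%/30% | 28.4, 1.94 | 63.7 v 37.7 | 25.9, 1.69 |
| 30%/10% | 6.8, 1.18 | 60.2 v 41.5 | 18.7, 1.45 |

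(Differences are in points and come from unrounded rates.) Constant-rate instead of uniform dropout gives nearly the same: 25.7 points and 1.68 for 10%/30%, and 18.9 points and 1.45 for 30%/10%.

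**No true effect** (43% in both arms, 10%/30% dropout). The primary shows a spurious 8.6 points (38.7% v 30.1%). The sensitivity analysis shows 3.5 to 3.8 points. Under constant-rate dropout it rejects about 8% of the time instead of 5%.

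**Is the selection the cause?** In a simulation of 2 million subjects per arm with the same independent dropout, removing every dropout, recurred or not, gave 22.0 points and 1.51 at 20%/20%, and 21.9 points and 1.51 at 10%/30%. The distortion comes from removing only those who had not recurred.

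**The case against.** A reader might infer that the analysis generally exaggerates the effect and offers false reassurance. The documents do not support that, for four reasons.

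- **Scale.** With equal missingness the odds ratio is unchanged in Case 1, the risk difference barely moves, and with no true effect both arms shift alike, so the test is not distorted. Only the success relative risk inflates. This stands, although relative risk is the measure the SAP reports.
- **Comparator.** In both unequal-dropout rows the sensitivity result is nearer the truth than the primary. At 10%/30% it would show, correctly, that the primary is too favourable. This stands, but it still misses the truth by 3.9 points, and under equal missingness the primary has the better relative risk.
- **Other evidence.** The per-protocol set requires TOC data whether or not the subject recurred, and SAP 8.2.1 plans Kaplan-Meier curves that censor recurrence-free dropouts. Both are partial checks. The per-protocol set is also limited to mITT subjects without major deviations and reuses SAP 4.4.1. The Kaplan-Meier plan gives medians and curves with no between-arm test, and censors at the last assessment before the first missed one.
- **Wording.** The second trigger in SAP 4.4.1 and the routing sentence in SAP 8.1.1 do not repeat the no-earlier-failure condition, and Protocol 18.6.2 removes anyone with missing values. If all such subjects were removed, the selection would shrink or vanish. I still think my reading is the natural one: the condition opens the SAP 4.4.1 rule, SAP 8.1 makes any recurrence by TOC a failure in its own right, and SAP 8.2.1 says for the secondary endpoints that "any clinical assessment outcomes at or before the specified visit will be counted". The ambiguity is itself a reason to state who is removed.

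**Conclusion.** The point holds on the natural reading of SAP 4.4.1, 8.1 and 8.1.1. The analysis selects on the outcome and discards some subjects who meet the plan's own definition of success.

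Under equal missingness the effect is modest: no more than about 0.4 points on the difference, and a relative risk of 1.53-1.59 (10% to 30% dropout) or 1.62 (5% per contact) against a true 1.51. Under unequal dropout the direction follows the arm that loses more subjects: overstated at 25.9 points and 1.69 for 10%/30%, understated at 18.7 points and 1.45 for 30%/10%. Overstatement is possible, not certain, and the primary rule is further from the truth in both of those cases.

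These sizes rest on the planning rates, on illustrative missingness rates, on a constant recurrence hazard and on missingness independent of recurrence. The primary analysis itself does not depend on this change, but its missing-data check should be put right before unblinding.

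**What to change.** Change the sensitivity analysis in SAP 8.1.1 as follows.

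1. Count a subject with a TOC evaluation and no recorded recurrence as an observed success whatever interim contacts were missed, as SAP 8.1 defines.
2. For subjects without TOC, replace deletion with a between-arm comparison of Week-24 recurrence-free probabilities. Use Kaplan-Meier estimates with a confidence interval for the difference, censoring recurrence-free subjects without TOC at their last assessment and not censoring TOC attendees at a missed interim contact. Multiple imputation is an acceptable alternative.
3. State explicitly how subjects who recur and also have a missed assessment or withdraw are classified.

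The Week-24 comparison is new. SAP 8.2.1 does not plan it, and its rule of censoring at the first missed assessment would have to differ here. The cost is SAP wording and one additional analysis of data already collected.

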## 8.2. Secondary Efficacy Endpoints

### 8.2.1. Clinical Response

The same inferential analysis employing the same methods as for the primary analysis will be performed for ITT, mITT, and PP sets to assess below endpoints.

- The percentage of subjects with no Mycologically Proven Recurrence (defined as an episode of VVC with a total composite score  $\geq 3$  on the Vulvovaginal Signs and Symptoms [VSS] Scale and a culture positive for Candida spp. that required antifungal treatment) up to Week 4, Week 8, Week 12, Week 24 (TOC), and Week 36 (end of follow-up [EOFU]);

- The percentage of subjects with no Mycologically Proven, Presumed or Suspected Recurrences up to Week 4, Week 8, Week 12 and Week 36 (EOFU);
- The percentage of subjects with no Mycologically Proven or Presumed Recurrences up to Week 4, Week 8, Week 12, Week 24 (TOC) and Week 36 (EOFU);

For each specified timepoint, any clinical assessment outcomes at or before the specified visit will be counted. The imputation rules described in [Section 4.4.1](#) will be used for the NRI analyses.

Analysis of time to first recurrence (Mycologically Proven, Presumed or Suspected) and time to first Mycologically proven recurrence of VVC through EOFU will use Kaplan-Meier method to estimate the median recurrence time and its 2-sided 95% CIs based on the ITT, mITT, and PP sets. The time to first recurrence (Mycologically Proven, Presumed or Suspected) and time to first Mycologically proven recurrence of VVC is defined as time (days) from first dose of study drug to the first recurrence (Mycologically Proven, Presumed or Suspected) and first Mycologically proven recurrence of VVC, respectively. Subjects who completed the study will be censored at the last visit date if no previously recurrence of VVC experienced. Subjects who discontinued early will be censored at the last available assessment if no previously recurrence of VVC experienced. Subjects who missed any required assessment of potential recurrence will be censored at the last available assessment before the first missed assessment if no previously recurrence of VVC experienced. If there was no post-baseline assessment of potential recurrence, subjects will be censored at the first dose date of study treatment.

Kaplan-Meier curves for time to the first recurrence (Mycologically Proven, Presumed or Suspected) of VVC and time to first Mycologically proven recurrence will be provided by treatment group based on the ITT, mITT, and PP sets.

The summary of the absolute number of recurrences from Baseline (Day 1) to Week 24 (TOC) and Week 36 (EOFU) will be presented by recurrence categories and overall, a two-way analysis of variance (ANOVA) model including effects for treatment group and Country will be performed. For individual treatment group and ibrexafungerp 300-mg BID comparison versus placebo, the least squares mean, associate standard error (SE), 95% confidence interval and corresponding p-value will be presented. Additionally, same analysis will be performed to only include those subjects who completed the specified visit based on the ITT set.

For the below ordered categorical endpoint, a proportional odds model will be fitted accounting for the effects of treatment, Country, and uncontrolled diabetes mellitus (Yes or No) at baseline. The proportional odds model will fit an ordered regression model for the ordinal dependent variable as described by McCullagh (1980). If the assumption of proportional odds is violated, alternative analyses will be considered which require a weaker assumption. The p-value, relative risk and 95% CI will be presented in the ibrexafungerp 300-mg treatment group compared to the placebo arm.

- The proportion of subjects in four ordered categories related to the number of Recurrences (Mycologically Proven, Presumed or Suspected) of VVC from Baseline (Day 1) to Week 24 (TOC) and Week 36 (EOFU). The four categories of recurrence are defined as (i) 0 episode, (ii) 1 episode, (iii) 2 to 3 episodes, and (iv)  $\geq 4$  episodes

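### SAP 8.2.1 plans no between-arm test or effect estimate for time to first recurrence, and its one planned number may not be estimable in the active arm

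*SAP*

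**What the plan says.** Time to first recurrence of any category, through Week 36, is a secondary efficacy endpoint in Protocol 9.3 and SAP 3.2.3. SAP 8.2.1 applies the primary inferential method (CMH p-value, relative risk, 95% CI) to three bulleted sets of recurrence-free percentages. For time to first recurrence, and for time to first Mycologically Proven recurrence, it says only that the analysis "will use Kaplan-Meier method to estimate the median recurrence time and its 2-sided 95% CIs", with curves by treatment group.

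Protocol 18.6.2 states: "The efficacy parameters will be evaluated comparing the ibrexafungerp treatment group versus the placebo group". It names methods for continuous, categorical and ordered endpoints but none for a time-to-event endpoint. SAP section 11 lists no change for this endpoint. In the same SAP section the number of recurrences does get a between-arm model ("For individual treatment group and ibrexafungerp 300-mg BID comparison versus placebo"), and the ordered categories get a proportional odds model.

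The event time is "time (days) from first dose of study drug to the first recurrence", without saying which date marks the recurrence. There are three main censoring rules. For completers: "Subjects who completed the study will be censored at the last visit date if no previously recurrence of VVC experienced". Those who discontinue early are censored at their last available assessment, on the same condition. A subject who missed a required check is "censored at the last available assessment before the first missed assessment if no previously recurrence of VVC experienced". The order in which the rules apply is not stated.

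**The concern.** The confidence intervals in the plan belong to each arm's median, not to a difference between arms, and curves by arm are descriptive. As written, the endpoint would give no estimate of the treatment effect on time to recurrence. A median also needs half the arm to have had the event. In a prevention trial sized on 65% success in the active arm, that may not happen by Week 36. The report could then show a placebo median beside an active median marked as not reached, with nothing that compares the two.

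**Working it through.** **The plan's own figure.** SAP 4.1 gives 65% v 43%, 90% power and alpha 0.05, with about 240 subjects at 1:1 and Fisher's exact test. SAP section 4 makes tests two-sided. Enumerated exact power at 120 per arm is 0.909, so the stated size reproduces. No figure is given for time to first recurrence.

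**Assumptions for the illustration.** The 65% and 43% are Week 24 recurrence-free rates, the hazard is constant in each arm, 120 subjects per arm are followed to Week 36, and nobody drops out. None of these is stated in the documents.

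**Medians.** Median = 24 × ln 0.5 / ln S(24).
- Ibrexafungerp: 24 × 0.693 / 0.431 = 38.6 weeks, after the Week 36 end of follow-up.
- Placebo: 24 × 0.693 / 0.844 = 19.7 weeks.

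**Chance that the active median is reached.** S(36) = 0.65^1.5 = 0.524, so each woman has probability 0.476 of a recurrence by Week 36. The median is reached if at least 60 of 120 recur: P(Binomial(120, 0.476) ≥ 60) = 0.33. For placebo, S(36) = 0.43^1.5 = 0.282 and the median is almost certain to be reached. A proven recurrence is also a recurrence, so the median for the proven-only analysis cannot come earlier.

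**Sensitivity of that chance.**
- The primary analysis counts missing data as failure (SAP 4.4.1). SAP 8.1.1 extends this to "Subjects who have one or more of the required assessments of potential recurrence not completed prior to or at Week 24 (TOC) visit". If 5% to 20% of subjects are failures for that reason alone, S(24) = 0.65/0.95 = 0.684 up to 0.65/0.80 = 0.8125. The active median then moves to about 44 to 80 weeks, and the chance of reaching it falls.
- The constant hazard can also fail in the other direction, because dosing ends at Week 20. To reach the median, (0.65 − 0.50)/0.65 = 23% of women recurrence-free at Week 24 must recur by Week 36. A constant hazard gives (0.65 − 0.524)/0.65 = 19%.

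**Feasibility of a comparison.**
- Hazard ratio = ln 0.65 / ln 0.43 = 0.51.
- Events by Week 36 = 120 × (0.476 + 0.718) = about 143.
- Schoenfeld power = Φ(√143 / 2 × |ln 0.51| − 1.96) = about 0.98, unstratified; 93 events suffice for 90%.
- In simulation with 15% dropout by Week 36 and up to 5% of checks missed, the lowest power was 0.93.

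**Censoring rules side by side.** There are nine scheduled checks (Weeks 4 to 36, every four weeks; Weeks 16, 20, 28 and 32 by phone). A recurrence-free completer who missed only the Week 16 call is censored at Week 36 by the completer rule. By the missed-check rule she is censored at Week 12, if she had no unscheduled visit. The documents give no miss rate. With an assumed independent rate of 1%, 3% or 5% per check, 1 − (1 − q)^9 = 9%, 24% or 37% of subjects miss at least one.

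The condition on previous recurrence can mean before the censoring date or before the missed check. In simulation on the same assumptions, the reading before the censoring date leaves the active Week 36 estimate at 0.522 to 0.524 (true value 0.524). It drops about 6, 17 or 27 of the 143 documented first recurrences. The reading before the missed check lowers the estimate by 0.3, 1.1 or 1.8 points. The hazard ratio barely moves under either.

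**The case against.** The best defence is that the arms are already compared. CMH tests cover recurrence-free percentages at Weeks 4, 8, 12 and 36, and the primary analysis covers Week 24. A reader might infer that recurrence over time is never compared between arms; that is not so. What is missing is a summary for the time-to-event endpoint itself. The fixed-week tests do not supply it, since they count missed checks as failures and give relative risks visit by visit.

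It can also be said that Protocol 18.6.2 is a general statement, so the SAP breaks no specified time-to-event analysis. That stands. The case for change is that a better analysis is available at almost no cost. Treating the endpoint as one of the other continuous endpoints does not help, because the ANOVA, MMRM and ANCOVA models do not handle censoring.

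On censoring, a reader might infer a serious bias by taking the condition to mean no recurrence at any time on study. Only recurrence-free women would then be censored back. In simulation that lowers the active Week 36 estimate by 1.4 to 7.4 points, and it disagrees with the unbiased reading on whether the active median is reached in 11%, 33% or 51% of trials. The text does not support this. It makes the word previously redundant; the same condition is attached to each of three consecutive censoring dates; and SAP 4.4.1 uses parallel wording ("a subject who has not previously experienced a failure response of the endpoint of interest") that points to time order. Those figures are not the size of the problem.

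The missing precedence also has one sensible answer. Every treated subject either completes or discontinues, so the missed-check rule has effect only if it overrides the other two.

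**Conclusion.** The point holds as an analysis gap in a non-key secondary endpoint. No test, hazard ratio or contrast of Kaplan-Meier percentages is planned for time to first recurrence or time to first Mycologically Proven recurrence. The single planned number has roughly a one-in-three chance of being estimable in the active arm under a constant hazard, 65%/43% as Week 24 recurrence-free rates and no dropout. The chance is lower if those rates already include missing-data failures, and higher if recurrences accelerate once dosing stops. A comparison would be well powered at the planned size.

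The primary and key secondary conclusions do not depend on this. The censoring order, the condition on previous recurrence and the event date need a clarifying sentence each; none is a demonstrated bias. The event-date point is missing detail whose effect was not quantified: Protocol 14.18.2 prefers that antifungal treatment wait for the culture, so assessment and treatment-start dates can differ.

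**What to change.** In SAP 8.2.1, for both time-to-event analyses:
- Add a log-rank test and a Cox hazard ratio with 95% CI, stratified by Country and uncontrolled diabetes as in the primary analysis. With four countries (SAP 6.1) and two diabetes levels there are up to eight strata, so state how sparse strata will be pooled.
- Label the p-value nominal, since Protocol 18.0 plans no multiplicity adjustment.
- Report Kaplan-Meier recurrence-free percentages with CIs by arm at Weeks 12, 24 and 36 beside the medians. They stay interpretable if the median is not reached or the hazards are not proportional.

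As a minor clarification:
- State that the missed-check rule takes precedence over the completer and early-discontinuation rules.
- State that it applies whether or not a recurrence is documented after the miss, so that recurrence-free women are not selectively censored back.
- Define the event date.
- Add a sensitivity analysis that counts every documented first recurrence.

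The cost is SAP wording and routine programming before unblinding; no new data are needed.
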